--	--

	
trial will be collected prospectively and submitted to a central imaging vendor for archiving. These scans may be independently reviewed at a later time at the request of Lilly.
 
End of Treatment Visit and Extended Safety Observation Period: All patients must have the end-of-treatment visit 28 days after the last dose of study treatment (± 7 days) and extended safety observation period visits 60 and 90 days after the last dose of study treatment (± 7 days). The procedures should be conducted as described in the protocol and schedule of events (Appendix A).
 
Long-Term Follow-Up Period: All randomized patients will be followed for OS every 9 weeks (± 7 days) during the first year from the 90-day follow-up visit, every 12 weeks (± 7 days) during the second year, and every 16 weeks (± 7 days) thereafter. The survival follow-up will be conducted until death or study completion, whichever is first, whether or not trial treatment was administered. For patients who were randomized, but withdrew consent, survival (date of death) will be obtained by use of publicly available information.
 
Tumor assessment will be performed for all randomized patients every 9 weeks (± 7 days) during the study treatment and during the first year from discontinuation of the study treatment, every 12 weeks (± 7 days) during the second year, and every 16 weeks (± 7 days) thereafter. Tumor assessment will be repeated until disease progression, death, or receipt of new anti-cancer therapy, or until study completion, whichever is first, whether or not study treatment was administered.
 
Scans will include head and chest, abdomen, and pelvis (CAPs) and will be sent to the central imaging vendor for archiving and possible assessment at a later date. If clinical progression is suspected, all relevant clinical documentation is to be submitted to the central imaging vendor for archiving.
 
All randomized patients will be followed after the end-of-treatment visit for treated patients or after randomization for patients not treated, until study completion or death, whichever is first.
 
The Investigator (or designee) will acquire the following information from patients who were randomized:
 
 • Tumor assessment will be performed for all randomized patients every 9 weeks (± 7 days) during the study treatment and during the first year from discontinuation of the study treatment, every 12 weeks (± 7 days) during the second year, and every 16 weeks (± 7 days) thereafter. Tumor assessment will be repeated until disease progression, death, or receipt of new anti-cancer therapy, or until study completion, whichever is first, whether or not study treatment was administered. • Subsequent cancer treatments (all randomized patients). • Any serious adverse events (SAEs) considered to be related to trial treatment >90 days post last day of trial treatment, follow until resolution. • Date and cause of death (all randomized patients). 
Continued access: All patients remaining on AM0010 without disease progression following study completion (see Section 3.7) will be able to enter the continued-access period of the study, in which patients on study treatment who continue to experience clinical benefit may continue to receive study treatment until disease progression, death, unacceptable toxicity, or end of trial.

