7.10 Follow-Up Period

During the extended safety observation period, all randomized patients will be followed for safety 60 and 90 days (± 7 days) after the last dose of study treatment and monitored according to the SOA ([Appendix A](#)).

During the long-term follow-up period, all randomized patients will be followed for OS every 9 weeks (± 7 days) during the first year from the 90-day follow-up visit, every 12 weeks (± 7 days) during the second year, and every 16 weeks (± 7 days) thereafter. The survival follow-up will be conducted until death or study completion, whichever is first, whether or not trial treatment was administered.

For patients who were randomized, but withdrew consent, survival (date of death) will be obtained by use of publicly available information.

The Investigator (or designee) will acquire the following information from patients who were randomized:

- Tumor assessment will be repeated every 9 weeks (± 7 days) during the study treatment and during the first year from discontinuation of the study treatment, every 12 weeks (± 7 days) during the second year, and every 16 weeks (± 7 days) thereafter. Tumor assessment will be repeated until study completion, disease progression, death, or receipt of new anti-cancer therapy for patients who were randomized, and not treated or discontinue treatment before disease progression, and do not withdraw consent.
- Subsequent cancer treatments (all randomized patients).
- Any SAEs considered to be related to trial treatment, follow until resolution.
- Date and cause of death (all randomized patients).

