10.6.6 Adverse Events

Adverse events will be analyzed in terms of treatment-emergent AEs defined to be any AEs that begin or worsen in intensity after trial drug initiation through 90 days after the last dose of trial drug. All AEs will be coded based on MedDRA terms.

Descriptive statistics of safety will be presented using NCI-CTCAE v4.03 by treatment arm. All treatment emergent AEs due to any cause, treatment-related AEs, SAEs, treatment-related SAEs, and AEs leading to discontinuation from the trial treatments will be tabulated using the worst grade per NCI-CTCAE v4.03 criteria by system organ class and preferred

term. Additional summaries include AEs by intensity (Grade 1 to 4 or/and Grades 3 and 4). All AEs will be listed.

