15.0 APPENDICES

Appendix A – Schedule of Assessments

Assessments Both trial Arm 1 and Arm 2 will follow the same schedule of assessments unless otherwise noted.	Screening	Clinic Visit (Cycle)			End of Treatment	Extended Safety Observation Period	Long-Term Follow-Up
	Within 21 Days of Randomization	1, 3, 5, etc. ±3 Days	2 ±3 Days	4, 6, 8, etc. ±3 Days	28 Days ±7 Days from Last Dose	60 and 90 Days ±7 Days from Last Dose	
GENERAL and SAFETY AWARENESS							
Informed Consent	X						
Medical/Cancer History and Demographics	X						
Physical examination (include Ht [screening only] and Wt)	X	X			X		
Vital signs	X	X			X		
ECOG performance status	X	X			X		
12-Lead ECG	X	X			X		
Concomitant Medication	●				●		
Adverse Event	Post Randomization	●			●		
Survival ^a and Treatment Status							X
LABORATORY ASSESSMENTS							
Hematology, Chemistry	X	X	X	X	X		
aPTT and INR or PT	X	X	X	X	X		
Thyroid Function Test (TSH, T3, and T4)	X	X			X		
Pregnancy Test	X	X			X		
Urinalysis	X	X			X		
PD-L1 Status	X ^b						
Submission of tumor sample for biomarker research		X ^c					
TRIAL TREATMENT ARM 1 and ARM 2							
Arm 1 AM0010		Self-Administration QD SQ					
Arm 1 and Arm 2 Pembrolizumab		200 mg 30 min IV Q3W					
IMAGING ASSESSMENT							
Tumor Assessment ^d	Within 30 days of randomization	X				X	X
ADA, PK and Biomarker BLOOD SAMPLES							
ADA (required Arms 1 and 2) ^e		X	X	X	X	X	
PK (required Arm 1 and crossover) ^e		X	X	X	X	X	
Biomarkers (required Arms 1 and 2) ^f		X	X		X		

^a All randomized patients will be followed for OS every 9 weeks (±7 days) during the first year from the 90-day follow-up visit, every 12 weeks (±7 days) during the second year, and every 16 weeks (±7 days) thereafter. The survival follow-up will be conducted until death or the study completion, whichever is first, whether or not trial drug was administered.

^b A fresh tissue biopsy is only required if no archival tissue is available within 60 days of informed consent or unless approved by the Medical Monitor.

^c Mandatory tumor tissue sample for biomarker research should be submitted once the patient is enrolled (preferably from the same block used for PD-L1 testing).

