^d Tumor assessment will be performed for all randomized patients every 9 weeks (±7 days) during the study treatment and during the first year from discontinuation of the study treatment, every 12 weeks (±7 days) during the second year, and every 16 weeks (±7 days) thereafter. Tumor assessment will be repeated until disease progression, death, or receipt of new anti-cancer therapy, or until study completion, whichever is first, whether or not study treatment was administered. A baseline tumor assessment is required at crossover.

^e ADA and PK samples will be collected on Day 1 of Cycles 1, 2, 3, 4, every fourth cycle thereafter, and at end of treatment visit, and at the follow-up visits 60 and 90 days after the last dose of study treatment.

^f Specific biomarker blood collection tubes may vary by time point. See the Lab Manual for details.

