Appendix B – Continued-Access Period Assessments

	Continued-Access Treatment Visits ± 3 Days	Continued-Access Follow-Up Visits 28, 60, and 90 days ± 7 Days after the Last Dose of Study Treatment
Arm 1 AM0010	X	
Arm 1 and Arm 2 Pembrolizumab	X	
Adverse event	X	X
ADA ^a	X	X
PK ^a	X	X

^a ADA and PK samples will be collected on Day 1 of every 4th cycle during the continued access treatment visits and at the continued access follow-up visits 28-, 60-, and 90-days after the last dose of study treatment.

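### The 60- and 90-day visits are described as safety follow-up, but Appendix A marks only tumor assessment, ADA and PK at them

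*Protocol*

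**What the plan says.** The synopsis requires an end-of-treatment visit 28 days after the last dose, followed by "extended safety observation period visits 60 and 90 days after the last dose of study treatment", each with a window of 7 days either way. For what is done, it says: "The procedures should be conducted as described in the protocol and schedule of events (Appendix A").

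Section 7.10 gives the purpose: "During the extended safety observation period, all randomized patients will be followed for safety 60 and 90 days". Sections 3.5 and 7.2 say the same, and all three refer to the schedule of assessments. Section 7.9 lists procedures for the 28-day visit. No section gives a matching list for days 60 and 90. Sections 7.12 and 7.13 place PK and ADA samples there and nothing else.

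Appendix A has a column headed "60 and 90 Days ±7 Days from Last Dose". Its only marks are tumor assessment, ADA and PK.

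Three other places bear on the point:

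- Appendix B, under "Continued-Access Follow-Up Visits 28, 60, and 90 days", does mark adverse events.
- Section 10.6.6 defines treatment-emergent events as "any AEs that begin or worsen in intensity after trial drug initiation through 90 days after the last dose of trial drug".
- Section 8.1 asks that patients withdrawn for toxicity be followed for at least 90 days, or until drug-related toxicities return to grade 1 or baseline.

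**The concern.** The text sets up a 90-day safety period and leaves the content of its last two visits to a table. That table contains no general safety item for them. A site that works from the grid, as sites usually do, would take a tumor assessment if one is due, draw ADA blood (and PK in Arm 1 and crossover patients), and have met the schedule without a prompt to ask about adverse events or run a safety panel.

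Safety and tolerability is a secondary endpoint, and Section 3.4.2 includes laboratory, ECG, vital-sign and performance-status data in it. Several immune-related events in Table 4 (hepatic, thyroid, renal, glycemic), and the anemia that Section 6.4.1.1 attributes to AM0010, are found largely by laboratory test. Sections 7.11 and 9.1.1 record a laboratory abnormality as an AE once it is clinically significant, but that requires a test to have been done. At stake is how completely late events are captured, and whether the schedule supports the 90-day window that Section 10.6.6 intends to analyze.

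**Working it through.** The plan states no figure on this point, so there is nothing to reproduce. The check is a row-by-row reading of Appendix A and a day count.

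**1. Is the 60/90-day column read correctly?** Each row has seven visit columns: screening; Cycles 1, 3, 5; Cycle 2; Cycles 4, 6, 8; end of treatment; 60/90 days; long-term follow-up. The ADA and PK marks fall in the sixth. Footnote e confirms this independently: samples are taken "and at the follow-up visits 60 and 90 days after the last dose of study treatment". Sections 7.12 and 7.13 agree. The column is placed correctly.

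**2. What is marked in it?**

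| Appendix A rows | Last mark before long-term follow-up |
|---|---|
| Physical examination, vital signs, ECOG, ECG | End of treatment (day 28) |
| Hematology/chemistry, coagulation, thyroid function, pregnancy test, urinalysis | End of treatment (day 28) |
| Concomitant medication, adverse event (bullets) | End of treatment, as the table reads in extracted text |
| Tumor assessment, ADA, PK | 60/90 days |

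Of 16 visit-based rows checked, 3 are marked at 60/90 days. Of the 11 general safety rows in the first three lines, 0 are marked. Nine of those 11 use ordinary X marks and are firm.

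**3. How firm are the other two rows?** They are less firm. The AE row reads "Post Randomization" under screening, then a bullet under Cycles 1, 3, 5 and a bullet at end of treatment. The concomitant-medication row has bullets only at screening and end of treatment. Section 7.4.1 requires concomitant medications at Cycles 1, 3, 5 and so on, so that row cannot be read cell by cell. The bullets are probably the ends of a drawn line, and where the line ends must be checked on the page image.

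**4. How long is the stretch after the last marked safety assessment?**

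- Nominal: 90 − 28 = 62 days, and 62/90 = 69% of the period.
- Shortest with windows: (90 − 7) − (28 + 7) = 83 − 35 = 48 days.
- Longest with windows: (90 + 7) − (28 − 7) = 97 − 21 = 76 days.

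**5. What does the text still require in that stretch?** The synopsis calls for continuous AE and SAE reporting. Section 9.3 puts every AE after consent on the CRF, whether the investigator observes it or the patient reports it, with no stop at day 28. Section 9.1.1 follows serious, related or discontinuation-causing AEs until they resolve, stabilize or are explained, and monitors marked liver abnormalities back to normal or near baseline. None of these rules schedules a laboratory test, an examination or an AE enquiry at day 60 or 90 for a patient with no known event.

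**6. Do the analysis windows agree?** Section 10.6.6 counts TEAEs to 90 days after the last dose. The synopsis counts to 30 days after the last dose. SAP 6.6.2 counts to 30 days after treatment discontinuation, or any time if serious and related. The shorter windows leave out about 90 − 30 = 60 of the days that Section 10.6.6 includes.

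**The case against.** The best defense is that AE collection does not depend on the grid. Both visits are mandatory and described as safety follow-up. Reporting is continuous and has no day-28 stop. Section 13.3 ends concomitant-medication recording when a new anti-tumor treatment starts within 90 days, which implies that recording otherwise continues past day 28. The AE and concomitant-medication bullets may be a line whose end is lost in extraction. Appendix B schedules no laboratory panel at its follow-up visits either, so leaving one out of Appendix A may be deliberate. Under SAP 6.6.2, a non-serious laboratory event starting between days 31 and 90 would not enter the TEAE tables in any case.

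Much of this stands. A reader might infer from the blank column that there are no safety data at all between days 28 and 90, or that late events and non-recovery are recorded only if patients volunteer them. The documents do not support either. The continuous-reporting rule, the follow-to-resolution rules in Sections 8.1 and 9.1.1 and the ADA samples all apply in that stretch. Nor does it follow that the SAP's TEAE tables would look cleaner, because the SAP window mostly excludes these days.

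What the defense does not remove is the mismatch. The text sends sites to Appendix A for the content of two safety visits, and nine safety rows there are plainly blank. Appendix B, by marking AEs at days 28, 60 and 90, shows that AE review at these times is within the protocol's own practice.

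**Conclusion.** The point holds as a gap between schedule and text. As Appendix A reads, 0 of 11 general safety rows are marked at the 60- and 90-day visits, and nominally 62 of the 90 days (48 to 76 with windows) follow the last marked safety assessment. This is a lack of scheduled AE review and safety tests at two visits, not an absence of safety reporting. It mainly affects new events that are asymptomatic or found only by laboratory test; known serious or related events are followed under other sections.

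A reader might go on to multiply an assumed late-event rate by the 100 patients. The documents give no such rate, and the product would also assume that nothing is detected through continuous reporting, so no patient count can be derived.

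The conclusion rests on the X-marked rows, which are firm, and on the AE and concomitant-medication bullets ending at day 28, which is less certain. If the page image shows those lines running into the 60/90-day column, the AE part reduces to Section 7.10 listing no procedures, and the question about laboratory tests and examinations remains.

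**What to change.** 1. In Appendix A, mark AE and concomitant-medication review in the 60/90-day column, and list both in Section 7.10. For AEs this matches Appendix B and Section 10.6.6, and it supports the reporting rule in Section 9.3. The cost is one table column and one sentence. The visits already take place, so the added site work is small.
2. Reconcile Appendix A with Sections 8.1 and 10.6.6 on whether safety laboratory tests are done at these visits, and state the answer either way. This is a separate and more debatable addition. ADA blood is already drawn at both visits in both arms, so no extra visit would be needed. Safety tests run at local laboratories (Section 7.11), so the cost if added is two local panels per patient.
3. Reconcile the 30-day TEAE window in the synopsis and SAP 6.6.2 with the 90-day window in Section 10.6.6, so that the schedule and the analysis cover the same period. This is a text change only.

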	
Patients will be randomized in a 1:1 ratio into 1 of 2 treatment arms.
 
Arm 1: Patients will receive AM0010 as a subcutaneous (SQ) daily (QD) injection and pembrolizumab as intravenous (IV) infusion on Day 1 of a 21-day cycle.
 
 ○ AM0010 Dose 
 ▪ ≤ 80 kg body weight = 0.8 mg ▪ > 80 kg body weight = 1.6 mg ○ Pembrolizumab Dose 
 ▪ 200 mg over approximately 30 minutes IV infusion 
Arm 2: Patients will receive pembrolizumab as IV infusion on Day 1 of a 21-day cycle.
 
 ○ Pembrolizumab Dose 
 ▪ 200 mg over approximately 30 minutes IV infusion 
Trial sites will provide best supportive care per institution's standard of care, including concomitant medications.
 
Arm 1 and 2 dosing (QD for AM0010 and Q3W for pembrolizumab) will continue in the absence of disease progression, unacceptable toxicity, or the patient withdraws consent, whichever is first. Patients will be treated with a maximum of 35 cycles of pembrolizumab every 3 weeks or 2 years, whichever is longer.
 
At the time of documented disease progression (per Investigator assessment) patients in Arm 1 will be discontinued from the treatment period of the trial and patients in Arm 2 may crossover to receive treatment with AM0010 with pembrolizumab.
 
All randomized patients will be followed for OS every 9 weeks (± 7 days) during the first year from the 90-day follow-up visit, every 12 weeks (± 7 days) during the second year, and every 16 weeks (± 7 days) thereafter. The survival follow-up will be done until death or the study completion, whichever is first, whether or not trial drug was administered. For patients who were randomized, but withdraw consent, survival (date of death) will be obtained by use of publicly available information.
 
Tumor assessment will be performed for all randomized patients every 9 weeks (± 7 days) during the study treatment and during the first year from discontinuation of the study treatment, every 12 weeks (± 7 days) during the second year, and every 16 weeks (± 7 days) thereafter. Tumor assessment will be repeated until disease progression, death, or receipt of new anti-cancer therapy, or until study completion, whichever is first, whether or not study treatment was administered.
 
All computed tomography (CT)/magnetic resonance imaging (MRI) scans for all randomized patients enrolled in the trial will be collected prospectively and submitted to a central imaging vendor for archiving. These scans may be independently reviewed at a later time at the request of Eli Lilly and Company (Lilly).

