INTERIM ANALYSIS:	A planned interim analysis may be performed when the 50th randomized patient has been followed up for approximately 3 months. No statistical boundaries or alpha spending will be applied for this interim analysis as the primary purpose of this analysis is to assess safety and PK. At the time of interim data lock, all patients on study will continue on the study per protocol. See Table 6 for the schedule of analyses of key endpoints.
STATISTICAL METHODS: EFFICACY ANALYSES	All efficacy analyses will be based on the Intent-to-Treat (ITT) population, which includes all randomized patients regardless of whether the patient receives any study drugs or has any efficacy assessments. The primary efficacy endpoint is objective tumor response assessed according to RECIST v.1.1 criteria. The ORR will be summarized and compared using a Cochran-Mantel-Haenszel 2-sided test at a type I error rate of 10% stratified by tumor histology (squamous vs non-squamous.) Progression-free survival will be compared in the 2 randomized treatment arms using a 2-sided log-rank test, stratified by the tumor histology. Progression-free survival time will be summarized using the Kaplan-Meier method to estimate the median PFS and 95% confidence interval (CI). Overall survival will be summarized in the same manner as the PFS.
SAFETY ANALYSES	Safety Population includes all randomized patients who received any amount of study drug. Trial treatment exposure will be summarized. Adverse events will be summarized in terms of treatment-emergent events defined to be any event that begin or worsen in grade after first dose through 30 days after the last dose of trial drugs. Descriptive statistics of safety will be presented using NCI-CTCAE version 4.03 by treatment arm. All treatment-emergent AEs, due to any cause, treatment-related AEs, AEs leading to discontinuation from the trial treatments, SAEs, and drug-related SAEs will be tabulated using worst grade per NCI-CTCAE v4.03 criteria by system organ class and preferred term. On-trial lab parameters including hematology and chemistry will be summarized using the worst grade per NCI-CTCAE v4.03 criteria.

Table of Contents

CLINICAL TRIAL PROTOCOL	1
CONFIDENTIAL INFORMATION	1
PROTOCOL APPROVAL PAGE	2
PROTOCOL ACCEPTANCE PAGE	3
SUMMARY OF CHANGES	4
PROTOCOL SYNOPSIS	7
TRIAL GLOSSARY	21
1.0 BACKGROUND AND RATIONALE	24
1.1 Non-Small Cell Lung Cancer	24
1.2 AM0010 Background	25
1.2.1 AM0010 Mechanism of Action	25

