SAEs which are considered related to study drug occurring >90 days after last trial treatment must be reported on both a CRF and on a SAE Report Form (with an autopsy report if available).

Investigators are not obligated to actively seek AEs or SAEs in patients once they have discontinued (the patient summary CRF has been completed). However, if the investigator learns of any SAE, including a death, at any time after a patient has been discontinued from the study, and he/she considers the event reasonably possibly related to the study treatment or study participation, the investigator must promptly notify Lilly or its designee.

Lilly will periodically review evolving aggregate safety data within the study by appropriate methods.

If it is deemed to be in the best interest of the patient to start a new anti-cancer treatment prior to the follow-up visit, the visit duration may be shortened. In this case, the follow-up assessments should be completed prior to the initiation of the new therapy. If an anti-tumor treatment is initiated within 90 days of the last dose of trial treatment, the start date of this treatment should be documented on the appropriate CRF.

The Investigator must notify the IRB of SAEs occurring at the site and other AE reports received from Lilly/designee in accordance with local procedures/site IRB policies.

It will be left to the Investigator’s clinical judgment whether or not an AE is of sufficient severity to require the patient’s removal from treatment. A patient may also voluntarily withdraw from treatment due to what he or she perceives as an intolerable AE. If either of these occurs, the patient must undergo an end-of-treatment assessment and be given appropriate care under medical supervision until symptoms cease or the condition becomes stable. If the patient is permanently withdrawn from the trial or investigational product due to an SAE, this information must be included in either the initial or follow-up SAE Report Form or the End-of-Treatment CRF.

Study site personnel must report any treatment discontinuations that result from AEs to Lilly or its designee via eCRF, clarifying, if possible, the circumstances leading to the discontinuation of treatment.

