## 6. A Priori Statistical Methods

### 6.1. General Considerations

#### 6.1.1. Population

**Enrolled Population:** all patients who signed the informed consent form and were registered into the interactive web response system (IWRS).

**Intent-to-Treat (ITT) population:** all randomized patients per the IWRS.

Unless otherwise noted, all disposition analyses will be performed on the ITT population, all patient characteristic and efficacy analyses will be performed on the ITT population and all safety and exposure analyses will be performed on the Safety population.

All analyses will be performed by treatment arm. Unless otherwise noted, all analyses on the ITT population will be performed by assigned treatment arm and all analyses on the safety population will be performed by actual treatment received.

**Per-Protocol Population:** all patients who are in the safety population and have no important protocol deviations.

The important protocol deviations which will result in exclusion from the Per-Protocol population are listed below. This is not an exhausted list and may be amended over the course of the trial. The final list will be provided as an appendix to this SAP before performing the primary analysis of this study (i.e. approximately 6 months after last patient randomized).

- patients with disease histology other than NSCLC
- patients with European Cooperative Oncology Group (ECOG) >1 at baseline
- patients who received prior regimen in metastatic setting
- patients who do not have measurable disease at baseline
- patients receiving the incorrect randomized treatment assignment (any amount of duration)

**Response Evaluable Population:** all patients who are randomized and received any amount of study medication, have baseline adequate tumor assessment, and at least 1 post-baseline adequate tumor assessment.

**Safety Population:** all randomized patients who received any amount of study medication, AM0010 or pembrolizumab.

**PK Population:** all patients who are treated with available serum time-concentration data from randomized patients.

**Biomarker Population:** includes all patients who are treated with available biomarker data from randomized patients.

**ADA Evaluable population:** all patients who are treated (in safety population), have baseline ADA (anti-drug antibody) result, and at least one post-baseline ADA result.

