**6.6.2. Adverse Events**

Adverse event terms will be mapped using MedDRA. Adverse events will be graded according to the National Cancer Institute (NCI) – A Common Terminology Criteria for Adverse Events (CTCAE) v 4.03.

Pre-existing conditions are defined as AEs that begin prior to the first dose of study drug.

A treatment emergent adverse event (TEAE) is defined as any AE that begins between the day of first dose and 30 days after treatment discontinuation (or up to any time if serious and related to study treatment), or any pre-existing condition that increases in CTCAE grade between the day of first dose and 30 days after treatment discontinuation (or up to any time if serious and related to study treatment).

Related AEs in patients treated with AM0010 in combination with pembrolizumab are defined as either related to AM0010 or related to pembrolizumab or both AM0010 and pembrolizumab.

The following TEAE/serious adverse events (SAE) outputs will be produced:

- a. overview of TEAEs
- b. summary of TEAEs by Preferred Terms (PTs) (all grade and grade  $\geq 3$ )
- c. summary of TEAEs by System Organ Class (SOC) and PT (all grade and grade  $\geq 3$ )

- d. summary of TEAEs by PT and Maximum Grade
- e. listing of SAEs
- f. summary of SAEs by SOC and PT (all grade and grade  $\geq 3$ )
- g. listing of TEAEs leading to study treatment discontinuation

Summaries b, c, d, and f will be produced for the related TEAEs/SAEs.

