#### 6.7.4. Crossover Patients

Patients in Arm 2 (pembrolizumab) who crossover to Arm 1 (AM0010 in combination with pembrolizumab) following documented disease progression will be analyzed accordingly if data warrants.

For patients who crossover to Arm 1 after documented disease progression on pembrolizumab, time to progression while on pembrolizumab will be compared to the time to progression following crossover, where the time to progression following crossover is defined as the time from time of crossover to the earliest documented disease progression. The last available tumor assessment before crossover will serve as the baseline for disease assessment post crossover. If the number of events permits, time to progression before and after crossover will be summarized descriptively using the Kaplan-Meier method.

Patients who crossover to the AM0010 in combination with pembrolizumab are censored at time of crossover (ie, AEs occurring during treatment with AM0010+pembrolizumab are excluded or control arm (pembrolizumab) patents). An exploratory safety analysis may be conducted for the crossover patients including all adverse events starting from the date of first dose of AM0010+pembrolizumab.

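### No treatment-emergent AE definition ends at the start of next-line therapy, while Arm 2 counting ends at crossover, so all-cause safety tables may be uneven between arms.

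*Protocol*

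**What the plan says.** There are three definitions of a treatment-emergent event, all based on dates alone:

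- Protocol synopsis, Safety Analyses: "any event that begin or worsen in grade after first dose through 30 days after the last dose of trial drugs".
- Protocol 10.6.6: "any AEs that begin or worsen in intensity after trial drug initiation through 90 days after the last dose of trial drug".
- SAP 6.6.2: "any AE that begins between the day of first dose and 30 days after treatment discontinuation", with no time limit for events that are both serious and related.

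None mentions a new anti-cancer therapy. On attribution, SAP 6.1.1 states that, unless otherwise noted, "all analyses on the safety population will be performed by actual treatment received".

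One treatment switch does close AE counting. SAP 6.7.4 says: "Patients who crossover to the AM0010 in combination with pembrolizumab are censored at time of crossover". It applies to Arm 2 only. According to the synopsis, at documented progression Arm 1 patients leave the treatment period, whereas "patients in Arm 2 may crossover to receive treatment with AM0010 with pembrolizumab".

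The date needed for a cut-off is already collected. Protocol 9.3 says: "If an anti-tumor treatment is initiated within 90 days of the last dose of trial treatment, the start date of this treatment should be documented".

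**The concern.** The plan treats the start of a new therapy as a boundary for efficacy. It ends the response window (Protocol 10.2.1, SAP 6.5.2.1) and censors PFS (Protocol 10.2.2, SAP Table JZGC.6.1 rule 8). Safety has no matching rule. An event caused by next-line treatment, if it starts inside the window, enters the all-cause tables of the study regimen.

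The arms are also handled differently after progression. An Arm 2 patient who crosses over stops contributing events to the pembrolizumab column at that point. An Arm 1 patient who moves to another therapy keeps contributing until day 30 or day 90. Safety and tolerability is a secondary objective that SAP 4.2 frames as a comparison. All-cause TEAE, Grade 3 or higher and SAE summaries are planned outputs, so an uneven counting rule bears on how the combination's tolerability is read.

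**Working it through.** The documents state no figure for events on next-line therapy, so there is nothing to reproduce. The check has three parts.

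**1. Do the collection rules close the gap?** Protocol 9.3, and Protocol 3.7 for continued access, let the follow-up visit be brought forward when a new therapy is needed, with the assessments done first. Protocol 13.3 stops concomitant-medication recording once a new therapy starts, except for treatment of AM0010-related events. Neither rule says that AE recording stops or that later events are left out of the tables. They narrow the gap in practice but leave the definition unchanged.

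**2. How many next-line days can fall in the window?** Let W be the window length in days (30 or 90, from the documents) and g the days from last study dose to first dose of next therapy (assumed, since the documents do not give it). I take treatment discontinuation in SAP 6.6.2 to mean the last dose.

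Overlap = max(0, W − g).

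| g (days) | W = 30 | W = 90 |
|---|---|---|
| 14 | 30 − 14 = 16 | 90 − 14 = 76 |
| 21 | 30 − 21 = 9 | 90 − 21 = 69 |
| 28 | 30 − 28 = 2 | 90 − 28 = 62 |
| 42 | 0 | 90 − 42 = 48 |

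With a cut at the start of next therapy, every cell becomes 0 in both arms.

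**3. How is the overlap split between arms?** Let c be the share of Arm 2 patients stopping their assigned treatment who cross over, rather than go straight to another therapy (assumed). Suppose equal numbers stop in each arm and g is the same. Arm 2 then contributes (1 − c) for each unit in Arm 1.

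Arm 1 share = 1 / (1 + (1 − c)).

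| c | Arm 1 share |
|---|---|
| 0 | 1/2 = 50% |
| 25% | 1/1.75 = 57% |
| 50% | 1/1.5 = 67% |
| 75% | 1/1.25 = 80% |
| 90% | 1/1.1 = 91% |
| 100% | 1/1 = 100% |

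The equal-timing assumption matters. AM0010 is given daily and pembrolizumab every 21 days, so the last Arm 2 dose may fall earlier relative to the next therapy. As an illustration, take a lag of half a cycle (10.5 days) and g = 14. With no crossover, the Arm 1 share is 16/(16 + 5.5) = 74% for W = 30 and 76/(76 + 65.5) = 54% for W = 90. With c = 50%, it is 16/(16 + 2.75) = 85% and 76/(76 + 32.75) = 70%.

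**The case against.** Counting all-cause events over a fixed period after the last dose is a defensible convention. It loses no late study-drug event and needs no judgement about cause. Replacing it with a truncated window would make retention of late events depend on investigator attribution in an open-label trial. This stands, and it is why the fix adds a table rather than replacing one.

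The exposure is small under the SAP's own 30-day window. The end-of-treatment visit is due at 28 days, give or take 7, and assessments should precede any new therapy. This also stands: the point becomes material mainly under the 90-day definition in Protocol 10.6.6.

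Full AE capture after a new therapy cannot be assumed. As the text was extracted, the AE row in Appendix A shows no mark for the 60- and 90-day visits, although Protocol 3.5 says patients are followed for safety then and Appendix B marks AEs at its follow-up visits. The table may have been damaged in extraction, so this settles nothing either way.

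Safety reporting is descriptive, with no test, and separate related-event summaries are planned. These limit the consequences. They do not protect the all-cause tables, and attribution in the related tables is unblinded.

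A reader might infer that next-line toxicity is charged to the randomized arm. The SAP tabulates safety by treatment received; the two coincide unless a patient was given the wrong treatment. A reader might also infer that progressing Arm 1 patients must move to other therapy. Protocol 7.6 allows treatment beyond initial progression, and some patients may receive nothing further.

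**Conclusion.** The gap is real. Whichever window applies, no definition closes at next-line therapy, and the only switch that ends AE counting is Arm 2 crossover. Following the plan exactly can therefore count next-line toxicity unevenly in the all-cause TEAE, Grade 3 or higher and SAE tables. The AM0010 arm carries more of it if crossover is common.

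The size cannot be fixed from the documents. It depends on the window length (9 against 69 overlap days for a day-21 start) and on crossover uptake, which is optional and not projected. A reader might infer that most of the excess falls on Arm 1, or that AM0010 would be made to look more toxic. Neither is established: with equal timing and no crossover the split is 50:50, and patients who leave Arm 2 directly for other therapy are affected in the same way.

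A percentage-point effect is also tempting. If 10% to 30% of Arm 1 started new therapy in the window, 20% to 40% of those had a Grade 3 or higher event, and half had none before, the rate would rise by 0.10 × 0.20 × 0.5 = 1 point to 0.30 × 0.40 × 0.5 = 6 points. That is 0.5 to 3 patients in 50. None of these inputs comes from the documents, nor do they distinguish 30 from 90 days, so the figure should not be used as an estimate.

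**What to change.** First, reconcile the 30-day window (synopsis, SAP 6.6.2) with the 90-day window (Protocol 10.6.6), since the length largely determines how much this matters.

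Then keep the planned all-cause tables and pre-specify in SAP 6.6.2 a second version of the TEAE, Grade 3 or higher and SAE summaries. Its window ends at the earlier of the chosen day limit and the day before the first dose of subsequent anti-cancer therapy. Retain the SAP's extension for serious related events, leave the crossover rule in SAP 6.7.4 as it is, and list the events that the cut excludes. Write the rule before the tables are produced, so that it cannot appear to have been chosen from the data.

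No new data are needed: the start date is already on the CRF, and SAP 6.4.5 already summarizes subsequent therapies. The cost is one extra set of tables. In these, a late study-drug event judged unrelated would be absent and would appear only in the main table and the listing.
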